### 6.2 DETAILS OF TRIAL PROCEDURES AT SELECTED VISITS

#### 6.2.1 Screening period

##### Informed Consent prior to trial participation:

All subjects must sign and date an Informed Consent consistent with ICH-GCP guidelines prior to trial participation. Please refer to [Section 8.1](#) for details.

##### Re-screening

Subjects who do not fulfil the eligibility criteria (i.e. subjects who do not fulfil all of the inclusion criteria or fulfil at least one of the exclusion criteria) are to be entered as screening

failure. Subjects are allowed to be re-screened twice based on investigator's judgment. Re-screening requires a new informed consent and unique study subject number

Details on particular observations and procedures at Visit 1 (screening visit):

Visit 1 will take place 3 to 28 days prior to randomization.

Observations and procedures will be performed as mentioned in [Flow Chart](#).

- Review of in-/exclusion criteria
- Demographics will be recorded
- Smoking status / calculation of pack-years
- Relevant medical history and baseline conditions
- Alcohol and drug screening
- Cotinine and skin prick test
- Complete physical examination will be conducted
- Body weight and height
- Vital signs measurement
- ECG recording
- Pulmonary function test
- Safety dipstick urine test
- Safety blood sampling and processing. [REDACTED]. For female subjects, pregnancy will be tested in serum.

- AE assessment
- Concomitant therapy documentation and recording, diet and lifestyle restrictions

### 6.2.2 Treatment period(s)

Details on particular observations and procedures at Visits 2, 3, 4, 5, and 6:

Observations and procedures will be performed as mentioned in the Flow Chart.

- Review of in-/exclusion criteria at Visit 2
- Smoking status to be checked at Visit 2, 4, and 6
- Alcohol screening and cotinine test at Visit 6
- Complete physical examination will be conducted at Visit 2, 4, and 6
- Body weight at Visit 2 and 6
- Vital signs measurement
- ECG recording at Visit 2, 4, and 6
- Pulmonary function test at Visit 2, 4, and 6
- Safety dipstick urine test at Visit 2, 4, and 6
- For female subjects, urine pregnancy testing will be conducted at Visit 2 (only if the time period between Visit 1 and Visit 2 exceeds 7 days), Visit 5 and Visit 6 prior to [REDACTED] bronchoscopy, respectively.

- Safety blood sampling and processing at Visit 2, 4, and 6. [REDACTED]
- Randomization will be conducted at Visit 2 after all safety measurements are completed (see [Section 4.1.2](#))

- Regarding administration of trial medication, dispense trial drug for home administration, collection of trial drug used at home, and use of diary please see [Sections 4.1.4](#) and [6.2.4](#))
- Treatment compliance check will be performed at Visit 3, 4, 5, and 6
- Subjects drug diary will be dispensed at Visit 2 and checked at Visits 3, 4, 5, and 6
- AE assessment
- Concomitant therapy documentation and recording, diet and lifestyle restrictions
- Bronchoscopy with LPS challenge and retrieval of BAL and biopsies will be performed at Visit 6. Pulse oximetry will be done during bronchoscopy. In case of female subjects, a negative urine pregnancy testing is required at Visit 6.

As this is a trial in healthy volunteers, no special care after the end of trial is needed.

### 6.2.3 Follow-up Period and End of Trial

[figure not shown]
#### Details on particular observations and procedures at Visit 7 and 8

Observations and procedures will be performed as mentioned in the [Flow Chart](#). Timing of Visit 7 in relation to Visit 6 is described in section [6.2.4](#).

- Complete physical examination will be conducted
- Alcohol screening at Visit 7
- Vital signs measurement
- ECG recording
- Safety dipstick urine test at Visit 8 including a pregnancy testing for female subjects
- Safety blood sampling and processing

- Treatment compliance check will be performed at Visit 7
- Subjects drug diary will be checked at Visits 7
- AE assessment

- Concomitant therapy documentation and recording, diet and lifestyle restrictions

- 
- Bronchoscopy with retrieval of BAL and biopsies will be performed at Visit 7, 24 hours ( $\pm 1$  h) after LPS challenge at Visit 6. In case of female subjects, a negative urine pregnancy testing is required at Visit 6. Pulse oximetry will be done during bronchoscopy. Trial is completed at Visit 8.

Subjects who took the trial medication and discontinue prematurely should undergo the EOT examination (Visit 8) as soon as possible after the last dose of trial drug.

#### 6.2.4 Timing for selected observations and procedures

[figure not shown]
On Day 1 (Visit 2), study participants will be admitted to the trial site and kept under close medical surveillance following drug administration. The subjects will then be allowed to leave the trial site after formal assessment and confirmation of their fitness.

On all other study days during treatment period, the study will be performed in an ambulatory fashion.

On Day 28 (Visit 6), subjects will stay at the investigational site for approximately 9 hours for PK sampling and bronchoscopy with LPS challenge and BAL as well as biopsy sampling. Prior to bronchoscopy, all relevant procedures according to [Flow Chart](#) will be performed.

On Day 29 (Visit 7), 24 hours after Visit 6, the second bronchoscopy with sampling of BAL and biopsies will be performed. Prior to bronchoscopy, all relevant procedures according to [Flow Chart](#)  will be performed. Subjects have to stay at the investigational site for approximately 8 hours and kept under close medical surveillance.

The time between tablet intake in the evening on Day 28 (Visit 6) and the bronchoscopy on Day 29 (Visit 7) should preferable not exceed 14 hours. Subjects are asked to take medication on Day 28 (Visit 6) as late as possible and ideally close to 10 p.m. The second bronchoscopy should be performed in the morning of Day 29 (Visit 7).

## 7. STATISTICAL METHODS AND DETERMINATION OF SAMPLE SIZE

### 7.1 STATISTICAL DESIGN - MODEL

#### 7.1.1 Objectives

The trial objectives are stated in [Section 2.2](#).

#### 7.1.2 Endpoints

The primary endpoint is the total neutrophil count in BAL 24 hours following endotoxin challenge, see [Section 5.1.1](#).

Secondary endpoints regarding BAL in the segment with endotoxin challenge are stated in [Section 5.1.2](#).

#### 7.1.3 Model

The statistical model used for the primary analysis of primary and secondary endpoints will be an analysis of variance (ANOVA) model on the logarithmic scale. This model will include the effect 'treatment' and is described by the following equation:

$y_{ik} = \mu + \tau_k + e_{ik}$ , where

- $y_{jk}$  logarithm of response (primary or secondary endpoint) measured on subject  $i$  receiving treatment  $k$ ,  $i = 1, \dots, 50$ ,  $k = 1, 2$ ,
- $\mu$  the overall mean,
- $\tau_k$  the  $k$ th treatment effect,
- $e_{ik}$  the random error associated with subject  $i$  receiving treatment  $k$ .

where  $e_{ik} \sim N(0, \sigma_B^2)$  i.i.d.

## 7.2 NULL AND ALTERNATIVE HYPOTHESES

This trial will be conducted to detect statistically significant differences between BI 1026706 and placebo in BAL neutrophil counts 24 hours following endotoxin challenge at the end of treatment.

The null and alternative hypotheses are

$H_0$ : geometric mean ratio of neutrophil counts at the end of the treatment is 1.

$H_a$ : geometric mean ratio of neutrophil counts at the end of the treatment is not equal to 1.

[figure not shown]
Safety and tolerability of BI 1026706 is to be determined on the basis of the safety assessments in comparison to placebo. It is not planned to test any statistical hypotheses with regard to these variables in a confirmatory sense. Instead, they will be described in their entirety and evaluated by descriptive statistical methods.

### 7.3 PLANNED ANALYSES

Measurements regarding BAL of a subject will be included in the analysis, if they are not flagged for exclusion, e.g. due to PD non-evaluability or a protocol violation relevant to the evaluation of these PD endpoints, which will be decided no later than in the Blinded Report Planning Meeting.

[figure not shown]
A PD endpoint regarding BAL may be considered as non-evaluable, if for example

- the amount of BAL was not sufficient,
- the LPS administration was not conducted as planned.

Detailed list of protocol violations will be provided in the TSAP.  
The statistical analysis will be based on the following analysis sets.

- Randomized set (RS):  
This subject set includes all randomized subjects, whether treated or not.
- Treated set (TS):  
The treated set includes all subjects who were randomized and treated with at least one dose of study drug. This is the full analysis set population in the sense of ICH-E9.

[figure not shown]

- Pharmacodynamic set (PDS):  
The pharmacodynamic set includes all treated subjects that have evaluable cell counts for the cell types defined in the primary or secondary endpoints following 24 hours of LPS administration.

### 7.3.1 Primary endpoint analyses

[figure not shown]
The primary objective of this study will be assessed using the primary endpoint, see [Section 7.1.2](#). The primary endpoint will be logarithmically transformed, and analyzed using the ANOVA as described in [Section 7.1.3](#). The least square means (LS means) of treatment difference and its 90% confidence interval (CI) on the log scale will be obtained from this model and will be exponentiated to obtain the geometric mean ratio and 90% CI in total neutrophil count between BI 1026706 and placebo on the original scale 24 hours post endotoxin challenge.

The primary analysis will be based on the PDS.

### 7.3.2 Secondary endpoint analyses

Secondary endpoints regarding BAL, see [Section 5.1.2](#), will be statistically assessed using the same methods as described for the primary analysis of the primary endpoint. The analysis will be based on the PDS.

#### 7.3.4 Safety analyses

Safety will be assessed for the further endpoints listed in [Section 5.1.3](#) as well as the further safety assessments described in [Section 5.3](#). All treated subjects (that is, all subjects who received at least one dose of study drug), will be included in the safety evaluation. Safety analyses will be descriptive in nature and will be based on BI guideline ‘Analysis and presentation of adverse event data from clinical trials’ (001-MCG-156).

The analyses will be done by ‘treatment at onset’.

Tabulations of frequencies/proportions will be used for the evaluation of categorical (qualitative) data, and tabulations of descriptive statistics will be used to analyze continuous (quantitative) data.

Measurements (such as ECG, vital signs, or laboratory parameters) or AEs will be assigned to treatments (see [Section 4.1](#)) based on the actual treatment at the planned time of the measurement or on the recorded time of AE onset (concept of treatment emergent AEs).

[figure not shown]
Therefore, measurements planned or AEs recorded prior to first intake of trial medication will be assigned to 'screening', those between first trial medication intake until the end of the REP will be assigned to ‘on-treatment’, and those between end of REP and end-of-trial examination will be assigned to ‘post-treatment’ and those after the end of trial examination will be assigned to ‘post-study’. These assignments including the corresponding time intervals will be defined in detail in the TSAP.

Additionally, further treatment intervals (analysing treatments) may be defined in order to provide summary statistics for time intervals, such as combined treatments, on-treatment totals or periods without treatment effects (such as screening and post-study intervals).

[figure not shown]
Adverse events will be coded using the MedDRA. Frequency, intensity and causal relationship of AEs will be tabulated by treatment, primary system organ class and preferred term. SAEs and other significant AEs (according to ICH E3), and AESIs will be listed separately (see [Section 5.3.7](#)).

Statistical analysis and reporting of adverse events will concentrate on treatment-emergent and drug-related adverse events. To this end, all adverse events occurring between start of treatment and end of the residual effect period will be considered ‘treatment-emergent’. Adverse events that start before first drug intake and deteriorate under treatment will also be considered as ‘treatment-emergent’.

Frequency, severity, and causal relationship of adverse events will be tabulated by system organ class and preferred term after coding according to the current version of the Medical Dictionary for Drug Regulatory Activities (MedDRA).

Relevant ECG findings will be reported as AEs.

#### **7.4 INTERIM ANALYSES**

No interim analysis is planned.

## 7.5 HANDLING OF MISSING DATA

Missing safety and pharmacodynamic data will not be imputed.

## 7.6 RANDOMIZATION

Subjects will be randomized in blocks to double-blind treatment in a 1:1 ratio, receiving either placebo or 100 mg BI 10276706 b.i.d. The block size will be documented in the CTR.

The sponsor will arrange for the randomization as well as packaging and labelling of trial medication. The randomization list will be generated using a validated system, which involves a pseudo-random number generator and a supplied seed number so that the resulting treatment is both reproducible and non-predictable. Access to the codes will be controlled and documented.

## 7.7 DETERMINATION OF SAMPLE SIZE

This is the first clinical trial conducted in healthy smoking subjects with 28-day exposure, and the sample size of 25 subjects per treatment group is considered sufficient to achieve the aims of this exploratory trial.

Hohlfeld et al. [\[R13-0305\]](#) investigated the effect of Roflumilast compared to placebo on the cell count of different cell types in BAL. Based on their results it is assumed that the mean neutrophil count 24 hours post endotoxin challenge in the placebo group is  $1256 \cdot 10^3/\text{ml}$  with a standard deviation (SD) of  $870 \cdot 10^3/\text{ml}$ . The mean number of neutrophils in the Roflumilast treatment group was  $836 \cdot 10^3/\text{ml}$  with SD of  $314 \cdot 10^3/\text{ml}$  and thus it was only 67% of that for the placebo group 24 hours post endotoxin challenge. This corresponds to a fold-change of 1.50 (placebo vs. roflumilast).

The sample size calculation is based on the following assumptions:

- The primary endpoint is log-normally distributed
- 1-sided significance level  $\alpha = 5\%$
- BI 1026706 will have a similar effect like Roflumilast. Hence a fold-change of 1.50 or in case of number of neutrophils is only 60% under BI 1026706 compared to placebo a fold-change of 1.67.
- The expected coefficient of variation (CV) is similar to the observed CVs in Hohlfeld et al.
- Based on Hohlfeld et al. the expected rate of neutrophil counts being unavailable due to reasons such as dropout, unqualified samples, discontinuation of procedure etc., is 10% to 20%.

[Table 7.7:1](#) below shows the expected power under the assumptions stated above and for various coefficient of variations (CV), evaluable subjects and fold-changes.

Table 7.7: 1 Expected power to detect differences in the treatments based on the primary endpoint for various coefficients of variation, evaluable subjects per group and expected fold-changes.

CV	N per group	Fold-change	
		1.50	1.67
0.38	20	96 %	99 %
	22	97 %	99 %
0.53	20	81 %	93 %
	22	84 %	95 %
0.69	20	64 %	81 %
	22	68 %	84 %

From the Table above, a sample size of 22 evaluable subjects per group will have at least 84% power to detect a significant difference in case the total cell count of neutrophils under BI 1026706 is at most 67% (corresponds to a 1.5 fold-change) of the respective number for placebo on original scale and the CV is not greater than 53%. To account for the potential 10% subjects without evaluable neutrophil counts, a total sample size of  $2 * 25 = 50$  subjects will be entered in the study.

The calculation was performed using the MTT0cv routine from the commercial software nQuery Advisor® Version 7.0 (Statistical Solutions Ltd., Cork, Ireland).

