7.4 PRIMARY ENDPOINT

As described in CTP Section 7.3.1, the primary analysis of the primary endpoint will be an analysis of variance (ANOVA) on the log-transformed scale, based on the PDS. The ANOVA model is described in CTP Section 7.1.3.

As described in CTP Section 7.2, the primary endpoint is subject of a confirmatory statistical hypothesis test, based on the primary analysis:

[figure not shown]
H_0 : geometric mean ratio, i.e. T/R, of the primary endpoint is 1.

H_a : geometric mean ratio, i.e. T/R, of the primary endpoint is not equal to 1.

H_0 will be rejected if its p-value is ≤ 0.1 .

H_a is a two-sided alternative hypothesis; testing this hypothesis at the 10% significance level is equivalent to using two one-sided tests, each at the 5% significance level.

No other confirmatory statistical hypothesis tests will be conducted in this trial.

Descriptive statistics and boxplots of the primary endpoint by treatment will also be provided.

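### Section 7.7 takes its roflumilast-like effect of 1.50 from raw means; on the geometric scale that is tested, the same figures imply about 1.32, for which power is about 55%, not 84%

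*Protocol*

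**What the plan says.** **What is tested.** Protocol Section 7.2 gives the null hypothesis as "geometric mean ratio of neutrophil counts at the end of the treatment is 1". Protocol Section 7.1.3 specifies an "analysis of variance (ANOVA) model on the logarithmic scale" with treatment as its only effect, which amounts to a two-sample t-test on logs. SAP Section 7.4 tests the same ratio and rejects at p ≤ 0.1, noting that "testing this hypothesis at the 10% significance level is equivalent to using two one-sided tests, each at the 5% significance level". This matches the "1-sided significance level" of 5% used for planning.

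**What is planned for.** Protocol Section 7.7 quotes a placebo mean of 1256 (SD 870) and a roflumilast mean of 836 (SD 314), in 10³/mL, from the cited segmental endotoxin study. It takes the second as 67% of the first and says: "This corresponds to a fold-change of 1.50 (placebo vs. roflumilast". The listed assumptions include "The primary endpoint is log-normally distributed", CVs similar to those observed in that study, and "BI 1026706 will have a similar effect like Roflumilast. Hence a fold-change of 1.50".

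**What is concluded.** From Table 7.7:1, "a sample size of 22 evaluable subjects per group will have at least 84% power to detect a significant difference", provided that the count on BI 1026706 is at most 67% of placebo on the original scale and the CV is at most 53%.

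**The concern.** The effect is taken from one scale and tested on another. For log-normal data the arithmetic mean exceeds the geometric mean by a factor that grows with the CV. When the placebo arm is the more variable one, part of a ratio of raw means reflects that extra spread and not a shift in the geometric mean. Section 7.7 makes the step from a roflumilast-like effect to 1.50 without conversion, although the SDs it quotes show clearly different CVs.

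At stake is how the result will be read. The trial is described as proof of mechanism, and SAP Section 7.4 calls the primary test confirmatory. A reader of Section 7.7 would conclude that a drug matching roflumilast fails to reach significance about 16% of the time. On the tested scale the same source figures put that nearer 45%.

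**Working it through.** **Inputs (all Protocol Section 7.7).** Placebo 1256, SD 870; roflumilast 836, SD 314; log-normal endpoint; one-sided 5%; 22 or 20 evaluable per arm. That these are arithmetic means is inferred: the SDs are in raw units, SD/mean reproduces the table's CVs of 0.69 and 0.38, and the section calls the 67% an original-scale figure.

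**1. Reproduce the stated power.** Two-sample t-test on logs, log-SD σ = √ln(1 + CV²), noncentrality = ln(ratio) / (σ√(2/n)), 2n − 2 degrees of freedom.
- CV 0.53: σ = √ln(1.2809) = 0.4976.
- Ratio 1.50, n = 22: 0.4055 / (0.4976 × √(2/22)) = 0.4055 / 0.1500 = 2.70.
- Critical t on 42 df = 1.682; power = 84.5%, against 84% stated.

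All 12 cells of Table 7.7:1 reproduce within about one point. The formula is sound, so the question is the input.

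**2. Put the cited figures on the tested scale.** Geometric mean = mean / √(1 + CV²); log-variance = ln(1 + CV²).

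| Arm | CV | Log-variance | Geometric mean |
|---|---|---|---|
| Placebo | 870/1256 = 0.693 | 0.3919 | 1256/1.2165 = 1032.5 |
| Roflumilast | 314/836 = 0.376 | 0.1320 | 836/1.0682 = 782.6 |

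Ratio = 1032.5/782.6 = 1.319 (0.758 active to placebo); ln = 0.2771. The ratio of raw means is 1256/836 = 1.502.

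**3. Power at the converted ratio, one-sided 5%.**
- n = 22, arms' own variances: SE = √((0.3919 + 0.1320)/22) = 0.1543; noncentrality = 0.2771/0.1543 = 1.80; power 54.8%. Simulation with unequal variances gives 55.0%.
- n = 20, arms' own variances: 51.5% (simulation 51.8%).
- Keeping the table's CV of 0.53: 56.8% at n = 22 and 53.4% at n = 20.
- Across the table's CVs at n = 22: 79% (0.38), 57% (0.53), 42% (0.69). None of them restores 84%.

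**4. Which input drives the loss.** With a true geometric ratio of 1.50 and the arms' own variances, power at 22 per arm is 83%. The change in effect size accounts for nearly all of the drop; the choice of CV accounts for about one point.

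**5. Detectable ratio.** 80% power at 22 per arm needs a geometric ratio of 1.46 (σ = 0.498) to 1.48 (pooled σ = √((0.3919 + 0.1320)/2) = 0.512), that is, about 0.68 active to placebo.

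**The case against.** **The 84% is conditional and correct.** Section 7.7 ties it to a 67% ratio and a CV of at most 53%. With one common CV the raw and geometric ratios are identical, so the figure is right for its condition. This stands. A reader might infer that 84% is a miscalculation; it is not. What fails is the attribution of 1.50 to roflumilast on the scale that is tested.

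**The 1.32 is a reconstruction.** It needs log-normality within each arm of the cited study and takes two sample SDs as true values. The documents give neither that study's geometric means nor its size. If both arms truly had a CV of 0.53, a CV ratio as extreme as the one seen, in either direction, would arise by chance in about 12% of studies with 10 per arm, 6% to 7% with 15, 4% with 20 and under 2% with 30; these sizes are assumptions. So the CV difference is plausible but not established, and 55% should carry that caveat. But Section 7.7 itself assumes log-normality and CVs like those observed, so 1.32 is what its own premises imply.

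**The trial is exploratory, and a null result will be read from the estimate and its 90% confidence interval.** This limits the consequences. It does not remove them, since the primary endpoint also has a prespecified test that the SAP calls confirmatory.

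Three further criticisms are tempting but unsupported:
- That CV 0.53 is wrong because neither arm showed it. It lies close to the pooled value (log-SD 0.512, CV 0.55), and step 4 shows that the choice hardly matters.
- That the upper end of the 10% to 20% loss range is ignored. Table 7.7:1 has rows for 20 per arm, and Protocol Section 3.3.5 provides for replacing subjects.
- That the 1.67 scenario needs the same conversion. It is a separate hypothetical (60% of placebo), and nothing ties it to CVs of 0.69 and 0.38.

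**Conclusion.** The point holds as a fault in the justification of the planning effect. Under the protocol's log-normal assumption, and with the quoted SDs taken at face value, a roflumilast-like effect is a geometric ratio of about 1.32. Power for it is about 55% with 22 evaluable per arm (57% at CV 0.53) and about 51% to 53% with 20. The 84% is the power for a true geometric ratio of 1.50 with a common CV of 0.53, a larger effect than the cited data imply on the tested scale.

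A reader might go on to infer that the trial has to be enlarged: 80% power at 1.32 would need about 41 to 43 evaluable subjects per arm. The documents do not require that. Section 7.7 presents 25 per arm as sufficient for an exploratory trial, and a sponsor may choose to power for 1.50. The plan should then say that this is what it has done.

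**What to change.** Revise Protocol Section 7.7 as follows:

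1. Keep 1.50 as the figure from the cited study, but state that it is a ratio of raw-scale means and equals the geometric mean ratio only if the two CVs are equal.
2. Label Table 7.7:1 and the 84% as conditional on a true geometric mean ratio of 1.50 or 1.67 with the same CV in both arms.
3. Add a scenario at a geometric ratio of 1.32: power about 55% at 22 per arm and 51% at 20. Note that it rests on log-normality in each arm and on the quoted SDs.
4. State the geometric ratio detectable with 80% power at 22 per arm: about 1.46 to 1.48, or about 0.68 active to placebo. A non-significant result can then be read against it.

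The cost is a change to text and one table. Subject numbers, endpoint, model and test stay as they are. The price is a less favourable power statement for a roflumilast-like effect.

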#### 3.3.5 Replacement of subjects

In case more than 6 subjects do not or are not expected to complete the trial (e.g. due to drop-out rate in the ongoing trial), the trial clinical monitor [REDACTED] and the trial statistician are to decide if and how many subjects will be replaced to ensure a sufficient number of evaluable subjects (as defined in 7.7). A replacement subject will be assigned a unique study subject number, and will be assigned to the same treatment as the subject to be replaced.

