Rationale for change		The drop-out rate in the trial after approximately 50% of subjects recruited into the trial is close to the cut-off point for replacement. To allow a seamless recruitment in the trial, replacement of subjects will need to start already prior to reaching the cut-off of maximum numbers of drop-outs. Spare reserve medication at the site will be used for this purpose which will require implementation of a trial-independent site-staff member with restricted access to randomization codes. This dedicated function will instruct the site's trial staff in a blinded manner which medication is to be dispensed to the replacement subjects.

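### Section 7.7 sizes the trial for the low end of its own 10% to 20% loss range, and the replacement trigger in Section 3.3.5 counts non-completers rather than subjects without an evaluable neutrophil count

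*Protocol*

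**What the plan says.** **Expected loss.** Among its planning assumptions, Protocol Section 7.7 states that "the expected rate of neutrophil counts being unavailable due to reasons such as dropout, unqualified samples, discontinuation of procedure etc., is 10% to 20" per cent. The rate covers subjects who leave and samples that fail.

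**Sample size.** Table 7.7:1 gives power for 20 and for 22 evaluable subjects per group. The conclusion takes 22 per group and at least 84% power for a 1.5 fold-change, provided "the CV is not greater than 53" per cent. It then goes to 25 per arm with the words "To account for the potential 10% subjects without evaluable neutrophil counts".

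**Replacement.** Protocol Section 3.3.5 opens with "In case more than 6 subjects do not or are not expected to complete the trial". The trial clinical monitor and the trial statistician then decide whether to replace and how many. The stated purpose is enough evaluable subjects, with a reference back to Section 7.7.

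**Evaluability.** Protocol Section 7.3 allows a BAL endpoint to be non-evaluable for reasons unrelated to completion, such as too little fluid or an LPS administration that did not go to plan. The decision is due no later than the Blinded Report Planning Meeting. Section 7.5 rules out imputing missing pharmacodynamic data. The primary analysis uses the pharmacodynamic set (Protocol Section 7.3.1; SAP Sections 6.3 and 7.4).

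**The concern.** There are two mismatches. First, the assumption is a range, but the sentence that justifies 50 subjects uses only its favourable end and gives no reason. A reader who takes only the conclusion away will believe that 22 per arm and 84% are what the plan expects.

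Second, the rule that should protect the evaluable number does not count evaluable subjects. A subject who attends every visit but gives an unusable Visit 7 lavage is a completer under Section 3.3.5 and a loss under Section 7.7. The threshold of 6 is exactly the gap between 50 entered and 44 needed, so it leaves no room for that kind of loss. Followed to the letter, the rule can let the evaluable number fall below its own target without anyone being asked to decide about replacement.

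**Working it through.** **Inputs.** From Protocol Section 7.7: log-normal endpoint; "1-sided significance level" of 5%; fold-change 1.50; CV 0.53; 22 evaluable per group; 10% to 20% unavailable; 25 entered per arm. SAP Section 7.4 tests two-sided at 10%, which is consistent: "testing this hypothesis at the 10% significance level is equivalent to using two one-sided tests, each at the 5% significance level". From Protocol Section 3.3.5: trigger at more than 6.

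**Reproducing the plan's power.** The log-scale SD is sqrt(ln(1 + CV²)) = sqrt(ln 1.2809) = 0.498. The effect is ln 1.5 = 0.405. The noncentrality is 0.405 / (0.498 x sqrt(2/n)), with 2n - 2 degrees of freedom and a one-sided 5% critical value.

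| n per arm | Noncentrality | Critical t | Power | Table 7.7:1 |
|---|---|---|---|---|
| 22 | 2.70 | 1.682 | 84.5% | 84% |
| 21 | 2.64 | 1.684 | 82.9% | not tabulated |
| 20 | 2.58 | 1.686 | 81.2% | 81% |
| 19 | 2.51 | 1.688 | 79.4% | not tabulated |

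The plan's figures are reproduced.

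**Reproducing the inflation.** 22 / 0.9 = 24.4, rounded up to 25 per arm, or 50 in total. This is correct for 10%.

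**What 50 entered gives across the stated range.**
- 10% loss: 25 x 0.90 = 22.5 per arm, so 22 and 84%.
- 15% loss: 25 x 0.85 = 21.25 per arm, so 21 and 83%.
- 20% loss: 25 x 0.80 = 20 per arm, so 20 and 81%.

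Twenty-two per arm holds only up to 3 losses in 25, which is 12%. If losses are independent and nobody is replaced, power averaged over the random number of losses is 85.1%, 83.1% and 80.9% at 10%, 15% and 20%. Chance variation in the losses therefore does not change the picture.

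**The trigger.** The decision opens at the seventh actual or expected non-completer. With 6, 50 - 6 = 44 remain, and 44 = 2 x 22. One unusable sample among these 44 leaves 43, so at least one arm is below 22 and no decision has opened. The documents give no separate rate for unusable BAL among completers, so the range below is an assumption, with an even split between arms.

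| Assumed unusable among 44 completers | Evaluable in total | Per arm | Power |
|---|---|---|---|
| 5% | 41.8 | 20.9 | 82.7% |
| 10% | 39.6 | 19.8 | 80.9% |
| 20% | 35.2 | 17.6 | 76.5% |

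At 10%, the total loss is 6 + 4.4 = 10.4 of 50, or about 21%, close to the top of the plan's range. Power drops clearly below 80% only when the unusable share goes beyond that.

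**The case against.** The plan has a good answer to much of this. The inflation is correct arithmetic for the rate it names. The 20-per-group rows of Table 7.7:1 are what 25 per arm becomes after 20% loss, so the lower figure is disclosed. The power statement is conditional on 22 evaluable subjects and is true as such; no sentence promises that 50 entered will deliver 22 per arm. Power stays above 80% over the whole stated range at CV 0.53, and the protocol calls the trial exploratory (although SAP Section 7.4 calls the primary test confirmatory). All of this stands and keeps the first mismatch small.

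On replacement, Section 3.3.5 names evaluable subjects as its aim and already looks ahead by including subjects not expected to complete. Some procedure-related losses also become non-completion, because Section 3.3.4.1 withdraws subjects from treatment for respiratory infections that could interfere with bronchoscopy or its analysis. Section 4.1.4.1, which Amendment 4 also changed, is not in the public text, so part of the procedure cannot be seen. This narrows the gap but does not close it: completers with unusable BAL are still outside the wording.

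A reader might go further and infer from the Amendment 4 rationale, where drop-out at about half of recruitment "is close to the cut-off point for replacement", that losses were already above 20% and power was heading below 80%. The documents do not support that. They give no count, and a drop-out rate of that size over 50 subjects would pass 6 and open the replacement decision. The same rationale says that replacement is to start before the cut-off is reached.

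**Conclusion.** The point holds as two mismatches of wording, and it is minor. In Section 7.7 the conclusion carries the 10% end of a 10% to 20% assumption. The full range gives 20 to 22 evaluable per arm and 81% to 84% power, a difference of about 3 points. That rests on fold-change 1.50, CV 0.53, a one-sided 5% test and no replacement. At CV 0.69 the plan's own table shows 64% against 68% for the same two sizes, a similar step from a lower level.

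The trigger in Section 3.3.5 matters more, because it allows a shortfall that the rule is meant to prevent. Six non-completers plus any unusable lavage among the rest puts the trial below 44 evaluable with no decision required. How far below depends on a rate that the documents do not give. Over an assumed 5% to 20%, power is about 83% to 76.5%.

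This is not an arithmetic error, and it does not show that the trial is underpowered.

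**What to change.** 1. **Section 3.3.5.** Keep the threshold at more than 6, but count every subject who does not have, or is not expected to have, an evaluable Visit 7 neutrophil count from the LPS-challenged segment. That means non-completers plus completers with non-evaluable BAL. Make the judgement blinded and while recruitment is open. Section 7.3 permits an early decision, and the planning meeting, which SAP Section 6.2 combines with database lock, is too late to replace anyone.

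2. **Section 7.7.** State that 50 entered with 10% to 20% loss gives 20 to 22 evaluable per arm and 81% to 84% power at CV 0.53 and fold-change 1.50.

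The cost is rewording in two sections, a slightly lower stated power, and possibly a few more of the replacements that the plan already allows. The planned number of 50 does not change. If the sponsor prefers to keep 22 per arm at 20% loss without relying on replacement, that takes 22 / 0.8 = 27.5, so 28 per arm or 56 in total; for a 3-point difference this is not needed.
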